8.1.2. Non-serious Adverse Events

All AEs that are not classified as serious.

8.2. Assignment of Adverse Event Intensity and Relationship to Investigational Product

The following guidelines and definitions should be used by the Investigator for the description of an AE when reporting information:

Nature of the AE :	Preferably an overall diagnosis or syndrome, rather than individual symptoms or signs. The Investigator must report adverse events using standard medical terminology. Any discrepancies between the subject's own words on his/her own records (e.g. diary card) and the corresponding medical terminology should be clarified in the source documentation.
Date of onset:	Date the AE started.
Intensity:	
Mild	The subject is aware of the sign or symptom (syndrome), but it does not interfere with his/her usual activities and/or it is of no clinical consequence.
Moderate	The AE interferes with the usual activities of the subject or it is of some clinical consequence.
Severe	The subject is unable to work normally or to carry out his/her usual activities, or the AE is of definite clinical consequence.
Actions taken :	All actions taken are to be noted
None	No other action was taken for this AE

Concomitant medication Drug treatment: the subject took a concomitant medication (either prescription or non-prescription) specifically for this AE

OR

existing concomitant medication dosage was modified as a result of this AE.

Hospitalisation or prolongation of hospitalisation The subject was hospitalised for this AE or subject's stay in hospital was prolonged because of this AE.

Therapeutic or diagnostic procedure Subject used other therapeutic measures (e.g. ice, heating pad, brace, cast, etc.) or subject underwent a diagnostic procedure (e.g., additional lab test, x-ray, etc.) for this AE.

Date of outcome: Date the AE abated. If the AE consists of several signs and symptoms (syndrome), the sign or symptom with the longest duration determines the duration of the AE. If the AE is marked "ongoing", the outcome date should be blank.

Outcome:

Resolved The AE is no longer present at any intensity - completely abated.

Resolved with sequelae The AE is resolved but residual effects are still present.

Worsened The AE is still present but at a heightened intensity. The rule of repetition of AE reporting should be applied.

Fatal This AE caused or directly contributed to subject's death.

Ongoing The AE is still present at the last contact with the subject.

Relationship to investigational product:

None only applicable when no investigational product was taken or when the subject is taking single-blind placebo, or when the AE can be ascribed with reasonable certainty to another cause.

Unlikely there are good reasons to think that there is no relationship, e.g. the AE is a known adverse drug reaction of a concomitant medication, or the same AE does not reappear after re-administration of the investigational product.

Possible equally valid arguments can be considered for or against an implication of the investigational product, e.g. the AE :

- follows a reasonable temporal sequence from the administration of the investigational product;
- follows a known or expected response pattern to the investigational product;
- but could readily have been produced by a number of other factors.

Probable	
the relationship is likely, e.g. the AE :
 
 • follows a reasonable temporal sequence from administration of the investigational product; • follows a known or expected response pattern to the investigational product; • is confirmed by improvement on stopping or reducing the dosage of the investigational product; • could not be reasonably explained by the known characteristics of the subject's clinical state.
Highly probable	
there is a strong relationship, e.g. the AE :
 
 • follows a reasonable temporal sequence from administration of the investigational product or in which the investigational product level has been established in body fluids or tissues; • follows a known or expected response pattern to the investigational product; • is confirmed by improvement on stopping or reducing the dosage of the investigational product, and reappearance of the AE on repeated exposure (rechallenge).

8.3. Collection and Reporting

The trial participant will be given the opportunity to report AEs spontaneously. A general prompt will also be given to detect AEs at each study visit after treatment has been administered, e.g., "Did you notice anything unusual about your health (since your last visit)?" (In order to prevent reporting bias, subjects should not be questioned regarding the specific occurrence of one or more AEs.)

If known, the diagnosis of the underlying illness or disorder should be recorded, rather than its individual symptoms. The following information should be captured for all AEs: onset, duration, intensity, seriousness, relationship to investigational product, action taken, and treatment required. If treatment for the AE was administered, it should be recorded on the appropriate CRF page. The Principal Investigator shall supply the sponsor and Ethics Committee with any additional requested information, notably for reported deaths of subjects.

Completion of supplemental CRFs may be requested for AEs and/or laboratory abnormalities that are reported/identified during the course of the study.

8.3.1. Serious Adverse Events

Following the subject's written consent to participate in the study, all SAEs must be collected, including those thought to be associated with protocol-specified procedures. All SAEs must be collected that occur within 30 days of discontinuation of dosing of the investigational product. If applicable, SAEs must be collected that relate to any later protocol-specified procedure. The Investigator should notify advanceCOR of any SAE occurring after this time period that is believed to be related to the investigational product or protocol-specified procedure.

Serious adverse events, whether related or unrelated to investigational product, must be recorded on the SAE page of the CRF and reported expeditiously to advanceCOR to comply

with regulatory requirements. An SAE report should be completed for any event where doubt exists regarding its status of seriousness.

All SAEs must be reported to advanceCOR within 24 hours after becoming aware of the event by confirmed facsimile transmission (fax) and mailing of the completed SAE page. In some instances where a facsimile machine is not available, overnight express mail may be used. If only limited information is initially available, follow-up reports are required. (Note: Follow-up SAE reports should include the same Investigator term(s) initially reported.)

If the Investigator believes that an SAE is not related to the investigational product, but is potentially related to the conditions of the study (such as withdrawal of previous therapy, or a complication of a study procedure), the relationship should be specified in the narrative section of the SAE page of the CRF.

If an ongoing SAE changes in its intensity or relationship to the investigational product, a follow-up SAE report should be sent immediately to the sponsor. As follow-up information becomes available it should be sent immediately using the same procedure used for transmitting the initial SAE report. All SAEs should be followed to resolution or stabilisation.

SAE Facsimile Transmission:

[name]

Local contact: [name]. med. [name] or [name]. med. [name] (Clinical Research Physicians)

SAE Mailing Address:

advanceCOR GmbH
Clinical Development Department
[name]
[name]
Germany

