
Title of study:
 
Revacept, an inhibitor of platelet adhesion in symptomatic carotid stenosis: A phase II, multicentre, randomised, dose-finding, double-blind and placebo-controlled superiority study with parallel groups.
	

Protocol identification (code or number):
 
Revacept/CS/02
	

OBJECTIVES
 
Efficacy objectives are:
 
 • Assessment of incidence of microembolic signals (MES) by transcranial Doppler (TCD) examination (before and after treatment) • Rate of MES per hour (before and after treatment) • Cerebral lesion analysis by DWI-NMR • Assessment of neurological status (NIH Stroke Scale) • Clinical endpoints will be summarised cumulatively i.e. before treatment, after treatment, at 3 months and at 12 months. The following endpoints will be recorded: 
 ○ Rate of all cause death ○ Rate of stroke-related death ○ Any TIA, amaurosis fugax or stroke including haemorrhagic stroke • Assessment of cardiovascular outcome including myocardial infarction and re-intervention up to 3 and 12 months 	

Safety objectives are to investigate whether Revacept compared to placebo induces adverse and serious adverse events.

Haemostasis will be closely monitored by assessing:

- laboratory parameters indicating thrombocytopenia and bleeding according to the RE-LY study group criteria
- where feasible: in vitro platelet function with collagen, TRAP and ADP-mediated platelet aggregation and in vitro bleeding time by PFA-100 / PFA-200

Pharmacokinetics of Revacept with respect to drug interaction with other antiplatelet drugs will also be assessed by determining plasma concentrations at various time points after administration of study medication for approximately 20 % of patients.

Methodology:

Multicentre, randomised 2:1, double-blind, placebo controlled, parallel groups, analysis. Blinded evaluation of efficacy and safety endpoints.

Treatment Regime:

Patients suffering from symptomatic carotid artery stenosis, transient ischemic attacks (TIAs), amaurosis fugax or stroke receive either Revacept (single dose) plus antiplatelet monotherapy (Aspirin or Clopidogrel) or monotherapy alone.

Patients receive a single dose of trial medication by intravenous infusion for 20 minutes. Patients are followed up one and three days after treatment, at 3 months and by a telephone interview at 12 months.

Treatment Groups:

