1.3. Data Safety Monitoring Board

The Data Safety Monitoring Board (DSMB) will consist of a statistician together with two independent neurologists who are scientifically well qualified, and who have personal experience of large multicentre studies and data monitoring activities.

Chairman:

[name]. med. [name]
[name]
[name]
[contact]
[contact]

Members:

[name]. [name]
[name]
[name]
[contact]
[contact]

[name]. rer. nat. [name]
[name]
[name]
[contact]
[contact]

The DSMB will hold regular meetings to review data concerning safety, efficacy and study performance. Unblinded data describing clinical endpoints, adverse events and laboratory values are to be compiled for these meetings by d.s.h. statistical services. The DSMB will

inform and advise the sponsor of all findings with regard to safety, efficacy and study performance. Review of data can lead the DSMB to a recommendation to the sponsor to stop the study. Minutes of Committee meetings will be recorded and filed. A special charter for the DSMB evaluation will be available. In accordance to GCP-V §13, SUSARS will be reported to the ethics committee, regulatory authority and the DSMB. If serious adverse events are more common in the experimental arm compared to the control arm the risk/benefit consideration will be reassessed. The Committee will inform the sponsor in writing if the frequency of serious adverse events including deaths exceeds 8 percent in one of the groups, and will advise concerning appropriate actions.

The first safety analysis will be performed by the DSMB once 10 patients have completed visit 5. The first 10 patients will be treated sequentially, e.g. only one patient is randomised at a time. The next patient will be randomised only once the first patient has completed visit 5 and no suspected unexpected serious adverse event has occurred (see also section 5.1). In addition, patient randomisation will be stopped by advanceCOR each time a serious adverse event occurs which is unexpected and possibly related to the study medication (SUSAR, see also section 8.3.2). Patient randomization will be resumed only if recommended by the DSMB. Thereafter, the DSMB will perform safety analysis at least annually.

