As for all antiplatelet drugs, it cannot be entirely excluded at this stage of development that Revacept could potentially increase bleeding propensity. Especially the likelihood of bleeding problems might occur in combination with multiple anti-thrombotic or antiplatelet drugs. In order to keep this risk low, concomitant oral anticoagulation and antiplatelet drugs other than anti-thrombotic monotherapy with Aspirin or Clopidogrel are prohibited in this study.

The immunogenicity of Revacept is judged to be considerably low, as its components are naturally occurring in the human body and should hence be recognised as 'self'. As for all therapeutic proteins, there is residual risk for Revacept triggering an aberrant immune reaction. Potential allergic responses may produce mild symptoms such as skin rashes and flue-like symptoms but also severe and potentially life-threatening reactions such as anaphylactic shocks. In order to minimise the risk of acute allergic reactions, patients with a history of allergic responses to intravenously administered drugs will be excluded from study participation. Furthermore, all patients will remain under medical supervision for 24 hours after receiving study medication.

Although the risk for production of anti-drug antibodies is low for single dose application, anti-Revacept autoantibodies could potentially cross-react with circulating platelets. For minimisation of this risk, patients with a known history of thrombocytopenia will not be

allowed to participate in this study. Furthermore, platelet counts and bleeding time will be closely monitored throughout the trial and blood samples for determination of anti-drug antibodies will be collected before and 3 months after exposure to study treatment.

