3. STUDY ENDPOINTS

The **efficacy endpoints** are:

- to evaluate whether the incidence of preoperative microembolic signals (MES) is reduced in patients with symptomatic carotid artery stenosis who have been treated with Revacept plus antiplatelet monotherapy (aspirin or clopidogrel) versus antiplatelet monotherapy alone (placebo). MES will be assessed by transcranial Doppler (TCD) examination.(before and after treatment)
- Rate of MES per hour (before and after treatment)
- Assessment of neurological status (NIH Stroke Scale)
- Cerebral lesion analysis by DWI-NMR and correlation to neurological status (before and after treatment)
- Clinical endpoints will be summarised cumulatively i.e. before treatment, one and three days after treatment, at 3 months and at 12 months. The following endpoints will be recorded:
 - Rate of all cause death
 - Rate of stroke-related death
 - Any TIA, amaurosis fugax or stroke including haemorrhagic stroke
- Assessment of cardiovascular outcome including myocardial infarction and re-intervention up to 3 and 12 months

Safety objectives

To assess safety, adverse events will be continuously recorded and be overseen by an independent Data Safety Monitoring Board (see section 1.3).

Safety will be summarised by treatment group and include the following:

- Vital signs
- ECG parameters
- Anti-drug antibody titres
- Reporting AEs including wound healing complications, laboratory abnormalities and use of concomitant medication
- Haemostasis will be closely monitored by assessing:
 - laboratory parameters indicating thrombocytopenia and bleeding according to the RE-LY study group criteria
 - where feasible: in vitro platelet function with collagen, TRAP and ADP-mediated platelet aggregation and in vitro bleeding time by PFA-100 / PFA-200

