7.1.6. Visit 6: follow up 3 months after treatment (\pm 1 month)

- Physical examination/ vital signs
- Review of concomitant medication
- Assessment of AEs including wound healing complications
- Assessment of neurological status (MRS, Barthel Index, NIH Stroke Scale)
- Assessment of clinical outcome
- ECG examination
- clinical biochemistry, clinical haematology (incl. assessment of bleeding according to RE-LY study group criteria), coagulation and urinalysis
- in vitro bleeding time PFA100 /PFA200 and platelet aggregation assay (response to collagen, ADP and TRAP)
- Pharmacokinetic blood sampling (for approximately 20 % of patients)
 - **T3m** 3 months (\pm 1 month) after IMP infusion
- detection of anti-Revacept antibodies

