APPENDIX B: DEFINITIONS OF CLINICAL EVENTS

Amaurosis fugax	transient monocular visual loss
Disabling stroke	functional disability of 3 or less points on the modified Rankin scale 30 days after symptom onset
Haemorrhagic stroke	new focal neurological deficit of vascular origin lasting more than 24 hours, proof of intracranial haemorrhage upon brain imaging
Ipsilateral stroke	stroke within the territory of the treated carotid artery
Ischaemic stroke	new focal neurological deficit of vascular origin lasting more than 24 hours, absence of intracranial hemorrhage upon brain imaging
Major adverse event	Death, stroke
Major stroke	initial stroke severity of 4 or more points on the NIHSS
Minor stroke	initial stroke severity of 3 points on the NIHSS
Myocardial infarction	
detection of rise and/or fall of cardiac biomarkers (preferably troponin) with at least one value above the 99th percentile of the upper reference limit together with evidence of myocardial ischaemia with at least one of the following
 
 • Symptoms of ischaemia • ECG changes indicative of new ischaemia (new ST-T changes or new left bundle branch block) • New onset of pathological Q waves in ECG • Imaging evidence of new loss of viable myocardium or new regional wall motion abnormality
Procedure-related death	any death within 30 days of the procedure or mortality resulting from a longer than 30 days hospitalisation because of the procedure
Procedure-related stroke	ipsilateral or contralateral stroke that has occurred within 30 days of the procedure
vascular death	death due to stroke, myocardial infarction or haemorrhage including deaths not non-vascular
technical CEA failure	failure to achieve <30% stenosis one day after CEA
restenosis	recurrent stenosis of $\geq 50\%$

REFERENCES

- Adams RJ and co-workers. Update to the AHA/ASA recommendations for the prevention of stroke in patients with stroke and transient ischemic attack. *Stroke*. 2008; 39: 1647-1652.
- Deutsche Gesellschaft für Neurologie. Recommendations for management of carotis stenosis.

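### Protocol 8.3.1 conflicts with itself, with 8.3, 8.3.3 and Visit 6, and with SAP 8.5.4 on whether SAEs after day 30 that are not believed related must be recorded

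*Protocol*

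**What the plan says.** **The limiting rule.** Protocol 8.3.1: "All SAEs must be collected that occur within 30 days of discontinuation of dosing of the investigational product". The Synopsis fixes when dosing ends: "Patients receive a single dose of trial medication by intravenous infusion for 20 minutes". For the time after the window, 8.3.1 continues: "The Investigator should notify advanceCOR of any SAE occurring after this time period that is believed to be related to the investigational product"; the same sentence extends this to events believed related to a protocol procedure.

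**The rules without a limit.** The opening of 8.3.1 requires collection of all SAEs once consent is signed and gives no end date. It then requires SAEs to go on the SAE page whether or not they are thought drug-related, and all SAEs to reach the sponsor within 24 hours. Section 8.3 prompts for AEs at every post-treatment visit and lists seriousness among the items recorded for each AE. Section 8.3.3 records all identified non-serious AEs, with no end date and no causality condition. Visit 6 (7.1.6) includes "Assessment of AEs including wound healing complications". Section 3 promises that "adverse events will be continuously recorded and be overseen by an independent Data Safety Monitoring Board".

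**Where the counts are used.** Under Protocol 1.3 the DSMB writes to the sponsor if the "frequency of serious adverse events including deaths exceeds 8 percent in one of the groups". SAP 8.5.4 tabulates AEs and SAEs reported at follow-up visits, by telephone or in writing, and gives an overview of patients with at least one SAE. Protocol 9.3 defines treatment-emergent events by their start only. None of these names a closing day.

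**The concern.** Taken literally, the 30-day sentence together with 8.3.3 gives an odd result. A mild unrelated AE on day 60 must be recorded, while a serious unrelated event on the same day need not be notified as an SAE. A site that follows the limiting sentence and a site that follows the unlimited ones would send different data for identical patients.

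Relatedness is also hard to judge in this period. The protocol names antibodies cross-reacting with platelets as a risk and says that "platelet counts and bleeding time will be closely monitored throughout the trial", but no routine visit or blood count is scheduled between Visit 5 and Visit 6, and the only post-dose antibody sample is taken at Visit 6. A blinded investigator deciding whether an intervening event is related has neither result from the schedule.

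At stake is whether the SAE percentage per arm means the same thing at every site, both for the DSMB and in the final report.

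**Working it through.** The plan states no figure on this point to reproduce. The check compares time windows and then lists which late events have another route into the data.

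**1. Length of the period in conflict.** Inputs: window of 30 days (8.3.1); dosing ends on the day of infusion (Synopsis); Visit 6 at 3 months ± 1 month (7.1.6). One month = 365.25/12 = 30.44 days.

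| Visit 6 at | Day | Days beyond 30 | Share of time to Visit 6 beyond day 30 |
|---|---|---|---|
| 2 months | 60.9 | 30.9 | 30.9/60.9 = 51% |
| 3 months | 91.3 | 61.3 | 61.3/91.3 = 67% |
| 4 months | 121.8 | 91.8 | 91.8/121.8 = 75% |

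These are shares of calendar time, not of events.

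**2. Gap between scheduled visits.** Latest intervention: day 3 + 5 = day 8. Latest Visit 5: 24 h + 24 h after that = day 10. The next scheduled visit is about day 61 at the earliest.

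**3. Late events with their own route, whatever the causality judgement.**
- Deaths: 8.7 (any randomised patient, no time limit) and 7.2.6 (to 12 months).
- Stroke, TIA, amaurosis fugax, myocardial infarction, re-intervention: 7.2.6, to 3 and 12 months.
- Bleeding: 7.2.11, assessed at every haematology visit including Visit 6, and reported under SAP 8.5.5.
- Related or procedure-related SAEs: 8.3.1, no time limit.

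What remains is the non-fatal, non-vascular, non-bleeding SAE after day 30 that is judged unrelated, for example a hospital admission for infection.

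**4. Why the form matters.** Section 10.11.1 puts the SAE fields on a separate form, and the AE page in 8.3.3 is for non-serious events. A site applying the 30-day limit has no clearly mandated form for the remaining group.

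**5. Sensitivity of the DSMB rule to the window (illustration).** With 50 planned per arm, 8% is 0.08 × 50 = 4, so more than 8% means at least 5 patients, reading the frequency as patients with at least one SAE. The documents give no SAE rate. Assume a constant monthly risk r. Then p(day 30) = 1 − (1 − r)^(30/30.44) and p(3 months) = 1 − (1 − r)^3, and the chance of at least 5 of 50 is binomial. The last column is 50 × [1 − (1 − r)^(61.3/30.44)].

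| Assumed r | P(≥5 of 50), to day 30 | P(≥5 of 50), to 3 months | Expected patients per arm with an SAE, day 31 to 3 months |
|---|---|---|---|
| 1% | <0.001 | 0.016 | 1.0 |
| 2% | 0.003 | 0.169 | 2.0 |
| 3% | 0.016 | 0.446 | 3.0 |
| 5% | 0.099 | 0.859 | 4.9 |

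The two probability columns contrast complete counting with no counting after day 30. The real effect is smaller, because the routes in step 3 recover part of the late events. SAEs clustering around the intervention would also raise the day-30 column. The table shows only that an unstated window changes how the rule behaves.

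**The case against.** The strongest reply is that 8.3.1 sets no clear cut-off at all. Its unlimited sentences, the AE prompt and the seriousness field in 8.3, the rule in 8.3.3 that an AE becoming serious is reported as an SAE, and SAP 8.5.4 all point to SAEs being picked up at Visit 6. Neither document applies a 30-day filter to the analysis. The DSMB also receives unblinded adverse events, clinical endpoints and laboratory values, not only SAE forms.

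Much of this stands. A reader might infer that late serious events are in fact counted less completely than mild ones. The documents do not support that: they show conflicting instructions, and a site following the Visit 6 prompt would capture these events.

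A reader might also infer that antibody-mediated harm would be missed. Platelets and bleeding are checked at Visit 6 without a causality condition, 7.1 provides for medically indicated extra testing, and the protocol rates the antibody risk after one dose as low.

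Nor does the procedure period reveal a loss. Appendix B counts "any death within 30 days of the procedure" as procedure-related, and with intervention on day 8 that period runs to day 38, 8 days past the SAE window. But deaths and strokes have their own routes, and procedure-related SAEs stay notifiable.

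The reply does not remove the conflict. The sentence on later related SAEs has no purpose unless later unrelated ones are treated differently, so a site can reasonably read the limit as binding.

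**Conclusion.** The point holds as a conflict between rules, with a narrow exposed group. For 31 to 92 days per patient, 51% to 75% of the time to Visit 6, the protocol gives two answers on whether an SAE not believed related must be recorded. Non-fatal, non-vascular, non-bleeding SAEs in that period may be under-counted or handled differently by site. The affected summaries are the DSMB's 8 percent rule and the SAP 8.5.4 overview, neither of which states a window.

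How many events this concerns cannot be derived from the documents; the monthly risks above are assumptions. The conclusion rests on the wording alone. CRF completion instructions or the DSMB charter, neither of which is among the documents, might settle the matter in practice. This is a worthwhile, inexpensive improvement and not evidence that safety data have been lost.

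**What to change.** 1. **Protocol 8.3.1.** Reconcile it with 8.3, 8.3.3 and the Visit 6 schedule: all SAEs regardless of causality from consent to Visit 6, and after Visit 6 only those believed related to the product or a protocol procedure. The 24-hour reporting time stays as it is.
2. **Protocol 1.3 and SAP 8.5.4.** State one counting window for the 8 percent rule and the SAE overview, and say whether the frequency counts patients or events.
3. **SAP 8.5.4.** Tabulate SAEs by arm up to day 30 and from day 31 to Visit 6 separately, so that any difference in completeness can be seen.

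The SAP, dated 10.06.2019, describes conduct in the past tense. If follow-up was already complete, item 1 can no longer change collection, but the SAP parts of items 2 and 3 can still be applied.

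**Cost.** Amendment wording and some extra SAE forms; no extra visit, since patients are already seen and asked about AEs at Visit 6. The reported SAE percentage will rise. The 8 percent notification may be reached more often, so its window must be explicit and the DSMB should agree it knowing this.
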